## **2.5.3 Handling of missing values/censoring/discontinuations**

[figure not shown]
### **Missing data**

Missing data for ACR20 response for data up to Week 16 will be handled as follows:

- Subjects who drop out of the trial for any reason will be considered non-responders from the time they drop out through Week 16.
- Subjects who do not have the required data at baseline and at the specific time point to compute response will be classified as non-responders.

### **Premature unblinding**

Patients who were unblinded prior to the scheduled timepoint will be considered non-responders from the time of unblinding up to the end of the placebo-controlled period (Week 24). The primary analysis will use this non-responder imputation.

## **2.6 Analysis of secondary objectives**

### **2.6.1 Secondary endpoints**

The secondary efficacy variables are listed below. Secondary efficacy variables will be analyzed using the FAS population unless otherwise specified.

- Change from baseline in van der Heijde modified total Sharp score at Week 24
- PASI75 response at Week 16
- PASI90 response at Week 16
- ACR50 response at Week 16
- Change from baseline in HAQ-DI© score at Week 16
- Change from baseline in DAS28-CRP at Week 16
- Presence of enthesitis at Week 16
- Presence of dactylitis at Week 16

### **2.6.2 Statistical hypothesis, model, and method of analysis**

#### **2.6.2.1 Overall Testing strategy to control type I error**

The following hypotheses will be included in the testing strategy, and type-I-errors will be set such that a family-wise type-I-error of 5% is kept:

##### **Primary objectives:**

- H1: secukinumab 300 mg is not different to placebo regimen with respect to ACR20 response at Week 16
- H2: secukinumab 150 mg is not different to placebo regimen with respect to ACR20 response at Week 16
- H3: secukinumab 150 mg No Load is not different to placebo regimen with respect to ACR20 response at Week 16

[figure not shown]
##### **Secondary objectives:**

- H4: secukinumab 300 mg is not different to placebo regimen with respect to structural damage (van der Heijde modified total Sharp score) at Week 24
- H5: secukinumab 150 mg is not different to placebo regimen with respect to structural damage (van der Heijde modified total Sharp score) at Week 24
- H6: secukinumab 150 mg No Load is not different to placebo regimen with respect to structural damage (van der Heijde modified total Sharp score) at Week 24
- H7: secukinumab 300 mg is not different to placebo regimen with respect to PASI75 response at Week 16 in the subset of subjects who have  $\geq 3\%$  skin involvement with psoriasis
- H8: secukinumab 150 mg is not different to placebo regimen with respect to PASI75 response at Week 16 in the subset of subjects who have  $\geq 3\%$  skin involvement with psoriasis

- H9: secukinumab 150 mg No Load is not different to placebo regimen with respect to PASI75 response at Week 16 in the subset of subjects who have  $\geq 3\%$  skin involvement with psoriasis
- H10: secukinumab 300 mg is not different to placebo regimen with respect to PASI90 response at Week 16 in the subset of subjects who have  $\geq 3\%$  skin involvement with psoriasis
- H11: secukinumab 150 mg is not different to placebo regimen with respect to PASI90 response at Week 16 in the subset of subjects who have  $\geq 3\%$  skin involvement with psoriasis
- H12: secukinumab 150 mg No Load is not different to placebo regimen with respect to PASI90 response at Week 16 in the subset of subjects who have  $\geq 3\%$  skin involvement with psoriasis
- H13: secukinumab 300 mg is not different to placebo regimen with respect to ACR50 response at Week 16
- H14: secukinumab 150 mg is not different to placebo regimen with respect to ACR50 response at Week 16
- H15: secukinumab 150 mg No Load is not different to placebo regimen with respect to ACR50 response at Week 16
- H16: secukinumab 300 mg is not different to placebo regimen with respect to the change from baseline in HAQ-DI® at Week 16
- H17: secukinumab 150 mg is not different to placebo regimen with respect to the change from baseline in HAQ-DI® at Week 16
- H18: secukinumab 150 mg No Load is not different to placebo regimen with respect to the change from baseline in HAQ-DI® at Week 16
- H19: secukinumab 300 mg is not different to placebo regimen with respect to the change from baseline in DAS28-CRP at Week 16
- H20: secukinumab 150 mg is not different to placebo regimen with respect to the change from baseline in DAS28-CRP at Week 16
- H21: secukinumab 150 mg No Load is not different to placebo regimen with respect to the change from baseline in DAS28-CRP at Week 16
- H22: secukinumab 300 mg is not different to placebo regimen with respect to presence of enthesitis at Week 16 in the subset of subjects who have enthesitis at BSL
- H23: secukinumab 150 mg is not different to placebo regimen with respect to presence of enthesitis at Week 16 in the subset of subjects who have enthesitis at BSL
- H24: secukinumab 150 mg No Load is not different to placebo regimen with respect to presence of enthesitis at Week 16 in the subset of subjects who have enthesitis at BSL
- H25: secukinumab 300 mg is not different to placebo regimen with respect to presence of dactylitis at Week 16 in the subset of subjects who have dactylitis at BSL
- H26: secukinumab 150 mg is not different to placebo regimen with respect to presence of dactylitis at Week 16 in the subset of subjects who have dactylitis at BSL
- H27: secukinumab 150 mg No Load is not different to placebo regimen with respect to presence of dactylitis at Week 16 in the subset of subjects who have dactylitis at BSL

---

The graphical approach of ([Bretz et al 2009](#)) for sequentially reject testing procedures is used to illustrate the testing strategy:

**Figure 2-1** Hierarchical testing strategy

The family-wise error will be set to  $\alpha=5\%$  and it will be controlled with the proposed hierarchical testing strategy. With this approach, the hypotheses will be separated into two families. The first family will include hypotheses of ACR20 at Week 16 and vdH-mTSS at Week 24 (H1 through H6). The Hypotheses of additional signs and symptoms (H7 to H24) will be the second family. The second family hypotheses will be tested only when all hypotheses in the first family have been rejected.

Each of the hypotheses (H1, H2 and H3) for the primary objective (ACR20 at Week 16) for each secukinumab regimen vs. placebo will be tested simultaneously at  $\alpha/3$ . Then based on the rejection of one or more (of H1, H2 and H3), the vdH-mTSS at Week 24 endpoint will be tested hierarchically for each dose (through H4, H5 or H6) at the level of  $\alpha/3$ . If anyone is rejected, then half (1/2) of  $\alpha/3$  will be passed on to each of the other two hypotheses of ACR20 if they were not already rejected.

If  $H_1$  to  $H_6$  in the first family are all rejected, then AIN457 300 mg for all variables in the second family will be tested hierarchically at  $\alpha$  starting from PASI75 ( $H_7$ ). If all variables in AIN457 300 mg group are rejected then test AIN457 150 mg group and finally AIN 457 150 mg No Load group for all variables in hierarchy. Of note, in the description above, rejection of a hypothesis refers to rejection of the two-sided hypothesis; however the level of a rejected hypothesis is only passed on according to the graphical procedure for the test of another hypothesis if the treatment effect is in favor of secukinumab.

### **2.6.2.2 Model and method of analysis**

#### **ACR50**

Response at Week 16 to ACR50 in the FAS will be evaluated using a logistic regression model with treatment and randomization stratum (TNF $\alpha$  status – naïve or IR) as factors and weight as a covariate.

The primary estimand of ACR50 response is the odds-ratio (each secukinumab dose vs. placebo) at week 16 in the FAS population that would be observed if all patients dropping out or being unblinded before week 16 or having with missing ACR50 data at week 16 were non-responders.

#### **Joint/bone structural damage (vdH-mTSS)**

[figure not shown]
The change at Week 24 from BSL van der Heijde modified Total Sharp Score (vdH-mTSS) will be evaluated using a non-parametric ANCOVA model with treatment regimen and randomization stratum (TNF $\alpha$  status – naïve or IR) as factors, and weight and BSL van der Heijde total modified Sharp score as covariates.

For subjects either on placebo or active, who have a missing vdH-mTSS score at Week 24, linear extrapolation will be used to impute the value at Week 24 if baseline and Week 16 assessments exist. For details about the derivation of the change from baseline see [Section 2.12.4.1](#).

For placebo subjects who meet the criteria for early escape at Week 16, they will be treated as missing for placebo treatment and linear extrapolation will be used to impute the value at Week 24. If BSL or all post- BSL vdH-mTSS values is/are missing for a subject, the subject will be excluded from the analyses.

[figure not shown]
Thus the primary estimand obtained is the difference in the vdH-mTSS scores (secukinumab dose – placebo) at week 24 in the FAS population with at least one baseline and post-baseline vdH-mTSS assessment that would be observed if the possibility for early escape at week 16 were not available to the placebo patient and patients with missing week 24 assessments experienced the same rate of disease progression as up to week 16.

[figure not shown]

- In addition the binary endpoint of no structural progression will be analysed to assess robustness of the results obtained with the primary estimand of the vdH-mTSS. After applying the linear extrapolation as described above no structural progression is defined as those subjects who have a change in vdH-mTSS at Week 24 relative to baseline  $\leq 0.5$ . The proportion of subjects without disease progression at Week 24 will be evaluated using a logistic regression model with treatment group and randomization strata (TNF $\alpha$  status – naïve or IR) as factors, weight and baseline vdH-mTSS as covariates.

The primary estimand for no structural progression is the odds ratio (secukinumab dose vs. placebo) of no structural progression rates at week 24 in the FAS population of patients with at least one baseline and post-baseline vdH-mTSS assessment that would be observed if the possibility for early escape at week 16 were not available to the placebo patient and patients with missing week 24 assessments experienced the same rate of disease progression as up to week 16.

### **Physical function (HAQ-DI©)**

Between-treatment differences in the change in HAQ-DI© will be evaluated using a MMRM with treatment, analysis visit and TNF-alpha inhibitor status as factors, and weight and BSL HAQ-DI© score as continuous covariates. Treatment by analysis visit and BSL by analysis visit will be included as interaction terms in the model. An unstructured covariance structure will be assumed for this model. The significance of the treatment effects for secukinumab regimens at different analysis visits will be determined from the pairwise comparisons performed between secukinumab regimens and placebo at the appropriate analysis visits.

The primary estimand for HAQ-DI is the estimated treatment differences (each secukinumab dose vs. placebo) at week 16 in the FAS population applying the MMRM model described above under the MAR assumption for any missing data.

### **Dactylitis**

Presence of dactylitis at Week 16 in the subset of subjects who have dactylitis at BSL will be evaluated using a logistic regression model with treatment and randomization stratum (TNF $\alpha$  status –naïve or IR) as factors and weight as a covariate.

The primary estimand for the presence of Dactylitis is the odds-ratio (each secukinumab dose vs. placebo) at week 16 in the FAS population that would be observed if all patients dropping out or being unblinded before week 16 or having with missing dactylitis data at week 16 were non-responders.

### **Enthesitis**

Presence of enthesitis at Week 16 in the subset of subjects who have enthesitis at BSL will be evaluated using a logistic regression model with treatment and randomization stratum (TNF $\alpha$  status –naïve or IR) as factors and weight as a covariate.

The primary estimand for the present of enthesitis is the odds-ratio (each secukinumab dose vs. placebo) at week 16 in the FAS population that would be observed if all patients dropping out or being unblinded before week 16 or having with missing ethesitis data at week 16 were non-responders.

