Presence of enthesitis at Week 16 in the subset of subjects who have enthesitis at BSL will be evaluated using a logistic regression model with treatment and randomization stratum (TNF α status –naïve or IR) as factors and weight as a covariate.

PASI75 and PASI90 response

PASI75 response and PASI90 at Week 16 will be evaluated for those subjects in whom the assessment occurred due to sufficient skin involvement (at least 3% BSA affected with psoriasis) (which is planned to be a subset of the FAS). These binary variables will be evaluated in the same fashion as ACR response, i.e. a logistic regression model with treatment and randomization strata as factors and weight as a covariate.

Changes in DAS28-CRP

Between-treatment differences in the change from baseline in DAS28-CRP will be compared by means of a MMRM with treatment regimen, analysis visit, and TNF-alpha inhibitor status as factors, and weight and BSL as continuous covariates. Treatment by analysis visit and BSL by analysis visit will be included as interaction terms in the model. An unstructured covariance structure will be assumed for this model. The significance of the treatment effects for secukinumab regimens at different analysis visits will be determined from the pairwise comparisons performed between secukinumab regimens and placebo at the appropriate analysis visits.

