## **Changes in DAS28-CRP**

Between-treatment differences in the change from baseline in DAS28-CRP will be compared by means of a MMRM with treatment regimen, analysis visit, and TNF-alpha inhibitor status as factors, and weight and BSL as continuous covariates. Treatment by analysis visit and BSL by analysis visit will be included as interaction terms in the model. An unstructured covariance structure will be assumed for this model. The significance of the treatment effects for secukinumab regimens at different analysis visits will be determined from the pairwise comparisons performed between secukinumab regimens and placebo at the appropriate analysis visits.

The primary estimand for DAS28-CRP is the estimated treatment differences (each secukinumab dose vs. placebo) at week 16 in the FAS population applying the MMRM model described above under the MAR assumption for any missing data.

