### **Presence of enthesitis**

If enthesitis is present with any of the 6 sites (lateral epicondyle humerus L + R, proximal achilles L + R and medial condyle femur L + R), the patient is counted as a patient with enthesitis.

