### **Dactylitis count**

The dactylitis count is the number of fingers and toes with dactylitis based on the LDI, with a range of 0-20.

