#### 4.2.2.2 Logistic regression

Certain binary outcome variables, e.g. response outcomes, will be evaluated using a logistic regression model with treatment regimen, weight, stratum if applicable. Odds ratios will be computed for comparisons of AIN457 regimens versus control(s) utilizing the logistic regression model fitted.

SAS code for logistic regression:

```
Proc logistic data=aaa;  
  Class TRT STRATA / param=glm;  
  Model AVAL = TRT WEIGHT STRATA;  
  Lsmeans TRT / diff cl exp;  
  Ods output diffs=lsm_diff;  
  Run;
```

Logistic regression will be applied to response variables at each visit.

In cases where logistic regression doesn't converge, Fisher's exact test will be applied for comparisons of between AIN457 doses. In this case, no odds ratios or confidence intervals will be estimated, but p-values may be calculated.

```
Proc freq data=aaa;  
  Table TRT * AVAL / fisher;  
  Where TRT in ("AIN457 xx mg" "Placebo");  
  Run;
```

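### The Week 16 enthesitis model omits the number of sites affected at baseline; adding it is a small, nearly free gain in precision, not a repair of validity

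*SAP*

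**What the plan says.** **The two models.** SAP 2.6.2.2 states for enthesitis: "Presence of enthesitis at Week 16 in the subset of subjects who have enthesitis at BSL will be evaluated using a logistic regression model". The dactylitis paragraph has the same form: "Presence of dactylitis at Week 16 in the subset of subjects who have dactylitis at BSL will be evaluated using a logistic regression model". In both, the terms are treatment, TNF stratum and weight. Protocol 9.5.1 has the same model for each, with treatment and stratum "as factors and weight as a covariate". The generic code in SAP 4.2.2.2 is "Model AVAL = TRT WEIGHT STRATA", again without a baseline term.

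**The baseline data.** SAP 2.12.4.1 defines presence of enthesitis as an any-site rule: "If enthesitis is present with any of the 6 sites", the patient counts as affected. The six sites are listed there. For dactylitis, "The dactylitis count is the number of fingers and toes with dactylitis based on the LDI, with a range of 0-20", and presence again means any digit. Protocol Table 6-1 schedules both assessments at baseline.

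**Other models in SAP 2.6.2.2.**
- HAQ-DI adjusts for weight and its baseline "score as continuous covariates".
- DAS28-CRP uses "weight and BSL as continuous covariates".
- The mTSS analysis of covariance includes baseline mTSS.
- The logistic model for no structural progression (mTSS change of at most 0.5) also includes baseline mTSS.
- The ACR20 (SAP 2.5.2), ACR50 and PASI75/90 logistic models have no baseline term.

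**The concern.** Presence of enthesitis holds every subject to the same all-clear standard. Someone who enters with one affected site must clear one; someone who enters with six must clear all six. ACR and PASI responses are percent improvements on each subject's own starting value, so a missing baseline term matters less there. The nearest relative in the plan is no structural progression: it too is a binary outcome with a fixed absolute cut-off, and its model does carry the baseline score.

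If the count is prognostic, leaving it out gives up some precision and leaves a chance imbalance in baseline extent in the estimate. The stake is modest but not confined to one test. Under SAP 2.6.2.1 every 300 mg variable in the second family must be rejected before any 150 mg variable is tested. A missed 300 mg enthesitis test (H22) would therefore close the second family for both 150 mg regimens.

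**Working it through.** **1. Inputs from the plan.** From the sample size sections (Protocol 9.7, SAP 3):
- Enthesitis: 79% on placebo, 58% on secukinumab; 0.60 × 330 = 198 and 0.60 × 220 = 132 subjects; two-sided 1.67%; stated power about 94%.
- Dactylitis: 85% and 50%; 0.50 × 330 = 165 and 0.50 × 220 = 110 subjects; stated power about 99%.

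**2. The plan's figures reproduce.** At 1.67%, exact enumeration of Fisher's test gives 94.8% for enthesitis (chi-square 95.4%) and 99.99% for dactylitis. At 5%, enthesitis power is 98.0% by Fisher and 98.3% by chi-square.

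**3. Inputs that must be assumed.** The documents give neither the distribution of baseline counts nor its effect on the outcome. I assume enthesitis counts of 1 to 6 with shares 20, 25, 20, 15, 10 and 10% (mean 3.0, variance 11.5 − 9.0 = 2.5, SD 1.58). The slope range is 0.2 to 0.6 log-odds per site. TNF stratum and weight are left out because no effects are given for them.

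**4. Is that slope range reasonable?** Suppose sites resolve independently, each with residual probability r. Then P(any site remains | k sites) = 1 − (1 − r)^k.
- Secukinumab: averaging to 58% needs r of about 0.28. Risk runs from 28% at one site to 1 − 0.72^6 = 86% at six. Slope = (1.82 + 0.94)/5 = 0.55.
- Placebo: averaging to 79% needs r of about 0.49. Risk runs from 49% to 1 − 0.51^6 = 98%. Slope = (4.02 + 0.04)/5 = 0.81.

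Correlation between sites within a patient would lower both, so 0.2 to 0.6 is not inflated. It remains an assumption.

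**5. Power with and without the count, enthesitis at 1.67%.** Simulated logistic Wald tests, 4,000 trials per row (simulation SE about 0.3 points), marginal rates held at 79% and 58%:

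| Odds ratio per site | Slope | Without count | With count |
|---|---|---|---|
| 1.00 | 0 | 95.2% | 95.2% |
| 1.25 | 0.22 | 95.0% | 95.4% |
| 1.50 | 0.41 | 95.7% | 96.8% |
| 2.00 | 0.69 | 95.4% | 97.8% |
| 3.00 | 1.10 | 94.8% | 99.0% |

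The last two rows lie above the assumed range. Measured as the squared ratio of mean |z|, the gain in effective sample size is about 1%, 6% and 12% at slopes 0.2, 0.4 and 0.6.

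**6. Cross-check by formula.** Power of 95.4% at 1.67% implies an expected z of 2.394 + 1.685 = 4.079. A gain g multiplies this by √(1 + g).

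| g | Expected z | Power at 1.67% | Power at 5% |
|---|---|---|---|
| 0 | 4.079 | 95.4% | 98.3% |
| 1% | 4.099 | 95.6% | 98.4% |
| 6% | 4.200 | 96.5% | 98.7% |
| 12% | 4.317 | 97.3% | 99.1% |

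**7. The level that applies.** If H1 to H6 are all rejected, SAP 2.6.2.1 tests the second family at the full 5%, and enthesitis (H22 to H24) belongs to it. Simulation at 5% gives 98.2% to 98.5% at slope 0.2 and 98.0% to 99.0% at slope 0.6, in line with the table above.

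**8. Chance imbalance.** The SE of the difference in mean counts is 1.58 × √(1/132 + 1/198) = 0.178, so 5% of trials differ by more than 1.96 × 0.178 = 0.35 sites in either direction. That shifts the log odds ratio by 0.35 × 0.2 = 0.07 to 0.35 × 0.6 = 0.21. The planned effect is ln(0.79/0.21) − ln(0.58/0.42) = 1.00.

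**9. Validity.** Under the null at nominal 1.67%, rejection rates were 1.80% without and 1.85% with the count at odds ratio 1.5, and 1.78% and 1.63% at odds ratio 2.0. All lie within simulation error (SE 0.2 points).

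**10. Dactylitis.** With assumed counts of 1 to 10 and odds ratios of 1.0 to 2.0 per digit, simulated power was 100% with and without the count (2,000 trials per setting).

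**11. Effect on the odds ratio.** For enthesitis it moves from about 0.37 without the count to about 0.31 with it at slope 0.6, because the odds ratio is not collapsible.

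**The case against.** The strongest reply is that this is a preference, not a defect. Protocol and SAP agree, randomisation protects the test, and every binary endpoint in the testing hierarchy (ACR20, ACR50, PASI75, PASI90) uses the same covariates without a baseline term. No structural progression is a robustness analysis outside H1 to H27, and its cut-off applies to a change from baseline, so it is a precedent rather than a rule. At 5% the enthesitis test already has about 98% power. Reaching it requires rejecting all three mTSS hypotheses, each planned at 83% power, which matters far more. The named estimand is an odds ratio, and adding a covariate changes what it measures.

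All of that stands, and it sets the size of the point. It does not remove the reason for the change: these outcomes, unlike ACR and PASI, make no reference to the subject's own baseline, and the data are already in hand. The planned odds ratio is also already conditional on TNF status and weight.

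A reader might infer more than the documents support:
- **That the planned test is biased or its error rate inflated.** It is not. Chance imbalance is covered by the nominal error rate.
- **That the count is a known strong predictor.** No visible text says so or gives an effect size; it is plausible from the any-site definition only.
- **That the plan breaks its own convention.** The continuous change models adjust for baseline, but the confirmatory binary models do not.
- **That no count-adjusted analysis is planned anywhere.** The exploratory and supportive sections are partly redacted, so this cannot be concluded.

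**Conclusion.** The point holds as a minor matter of efficiency. The enthesitis model leaves out a baseline count that can be derived from collected data and that the outcome plausibly depends on. For slopes of 0.2 to 0.6 log-odds per site and the assumed count shares, including it is worth about 1 to 12% in effective sample size. That is about 0 to 2 power points at 1.67% and about 0 to 1 point at 5%, where power is already about 98%. At the top of that range the chance of missing the 300 mg enthesitis test falls from about 2 in 100 to 1 in 100. For dactylitis, power already exceeds 99%, so the case there is consistency and correction of chance imbalance only. Every gain rests on assumed slopes and counts; with no association the gain is nil.

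**What to change.** In SAP 2.6.2.2 and Protocol 9.5.1, add the baseline number of affected enthesitis sites (1 to 6) to the enthesitis logistic model. Add the baseline dactylitis count (1 to 20) to the dactylitis model, and add the term to the SAP 4.2.2.2 code for these two endpoints. State that each count enters linearly on the log-odds scale, and how sites or digits not scored at baseline are handled. Amend the estimand sentences for both endpoints to say that the odds ratio is conditional on the baseline count as well as on TNF status and weight.

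Make the change before the clinical team is unblinded at the Week 24 database lock (Protocol 3.5). If that has passed, keep the planned models as primary and report the adjusted ones as supportive.

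The cost is one covariate per model and no new data. The small downside is the changed odds ratio (for example about 0.37 to 0.31 at slope 0.6), which makes comparison with unadjusted odds ratios from other studies less direct.
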